## **7.1 Specification of Safety Parameters**

The primary safety parameter used in this study is online versus in-person CST delivery. In addition, each session will have two facilitators who completed CST training, one who leads facilitation and one who monitors and supports participants throughout the discussion to address any challenges that may arise. Also, to protect confidentiality, methods to protect identifying information and participant data will include the use of password protected programs, encrypted software, and use of secured servers, and password protection into Zoom meetings. See section 2.3 for specific safety measures against loss of confidentiality and breach of privacy.

## **7.2 Methods and Timing for Assessing, Recording, and Analyzing Safety Parameters**

There are no documented harmful side effects from receiving a referral for or participating in CST (Orrell et al., 2017; Spector et al., 2003). Although the minimal risk of CST has been established and our online delivery further reduces risk for harm, care will be taken to assess, record, and analyze safety parameters.

V-CST facilitators will monitor participants for harm at all times during therapy delivery. Should a safety event occur, the event will be addressed by the PI upon receiving the adverse event report and reported to the Safety Officer.

## **7.3 Adverse Events and Serious Adverse Events**

Definitions for adverse events (AEs), serious adverse events (SAEs), and Unanticipated Problems (UP) to be used for this trial are provided below:

**Adverse Event (AE):** Any unfavorable medical occurrence in a clinical research study participant, including any abnormal sign (e.g., abnormal physical exam or laboratory finding), symptom, or disease, temporally associated with the participants’ involvement in the research, whether or not considered related to participation in the research.

**Serious Adverse Event (SAE):** Any adverse event that:

- Results in death,
- Is life threatening, or places the participant at immediate risk of death from the event as it occurred,
- Requires or prolongs hospitalization,
- Causes persistent or significant disability or incapacity,
- Results in congenital anomalies or birth defects,
- Is another condition which investigators judge to represent significant hazards.

**Unanticipated Problems (UP):** Any incident, experience, or outcome that meets all of the following criteria: unexpected, in terms of nature, severity, or frequency, given (a) the research procedures that are described in the protocol-related documents, such as the IRB-approved research protocol and informed consent document; and (b) the characteristics of the study population; related or possibly related to participation in the research; suggests that the research places participants or others at a greater risk of harm (including physical, psychological, economic, or social harm) than was previously known or recognized.

As stated above, one possible AE for this study is increased stress. For example, it is possible that the group discussion that takes place will increase participant stress. Increased stress is a possible mild AE of CST. This study has no other AEs.

No SAEs are expected. No AEs or SAEs of CST have been reported in over 15 years of studies. CST involves group discussions, and in this trial, CST will be delivered online to prevent infectious disease transmission.

Although hospitalizations and death or not uncommon in this population in general, they are unlikely to be related to the study. In the event of hospitalizations or death of V-CST participants identified by the V-CST facilitators, the lead facilitator will report this information to the referring physician per standard of care practice. In the event of hospitalizations or death of any study participant (intervention or control group) identified by the referral site, the referral site will report this information to the study coordinating site (UMass).

### 7.3.1 Reporting Procedures

No SAEs are expected to relate to participation in this study. Hospitalizations and death are expected in this population and will be assessed by the V-CST facilitators and referring sites but are not expected to be related to study participation. The minimal risk of participation in CST has been established through implementation of CST in numerous studies, which have concluded: “CST has no documented adverse effects and, therefore, risk to participants will be low” (Spector et al., 2019). Although the risks of participating in CST are established to be low, it is possible that the group discussion that takes place during CST will increase participant stress. Increased stress is a possible mild AE of CST. AEs will be reported to the PI and to the HCSs within 5 business days of their occurrence.

AEs will be reported per IRB policies and also to IMPACT Collaboratory Regulatory and Data Team for dissemination to the NIA IMPACT Collaboratory PO ([name]), and the project’s IMPACT Safety Officer, six months after the start of enrollment and again at the end of enrollment/data collection (whichever is later) , or at the frequency requested by NIA or the IMPACT Safety Officer.

Process for identifying AEs, SAEs, and UPs:

In the unlikely event of an AE, the lead facilitator will complete an adverse event form with supporting documentation of the event such as lab values, hospital/discharge summaries, and clinical evaluations to

be submitted to the patient's HCS within 5 business days of the incident. An IMPACT Collaboratory-approved report form will be used, with adaptations made as identified to be needed. The patient's referring provider will review the adverse event form and complete the form with a determination on relatedness and severity then submit documentation to the PI/UMass team within 5 business day from being notified of the incident.

Regarding adverse events that are serious and unexpected and unanticipated problems, the lead facilitator will follow the same procedure as for AEs and will be required to submit documentation immediately upon becoming aware of the incident.

All adverse event reporting will be done through a secure file transfer protocol established by the UMass IT services to ensure protected transfer of AE documentation. The PI or study coordinator will initiate communication with the sponsor to notify of an AE event per the reporting schedule below.

The following subsections include a discussion of how AEs will be classified. Data and safety monitoring reporting will classify SAEs and AEs as to their severity, expectedness, and potential relatedness to the study intervention as per the definitions below:

### **Severity**

- **Mild:** Awareness of signs or symptoms, but easily tolerated and are of minor irritant type causing no loss of time from normal activities. Symptoms do not require therapy or a medical evaluation; signs and symptoms are transient.
- **Moderate:** Events introduce a low level of inconvenience or concern to the participant and may interfere with daily activities, but are usually improved by simple therapeutic measures; moderate experiences may cause some interference with functioning.
- **Severe:** Events interrupt the participant's normal daily activities and generally require systemic drug therapy or other treatment; they are usually incapacitating.

### **Expectedness**

- **Unexpected** - nature or severity of the event is not consistent with information about the condition under study or intervention in the protocol, product brochure, or investigator brochure.
- **Expected** - event is known to be associated with the intervention or condition under study.

Unexpected events will be subject to expedited reporting requirements as described in the NIA Guidance on Clinical Trials.

### **Relatedness**

All adverse events (AEs) will have their relationship to V-CST assessed by a V-CST facilitator who examines and evaluates the participant based on temporal relationship and her clinical judgment. The degree of certainty about causality will be graded using the categories below.

- **Definitely Related:** The adverse event is clearly related to the investigational agent/procedure – i.e., an event that follows a reasonable temporal sequence from administration of the study intervention, follows a known or expected response pattern to the suspected intervention, that is confirmed by improvement on stopping and reappearance of the event on repeated exposure and that could not be reasonably explained by the known characteristics of the subject's clinical state.
- **Possibly Related:** An adverse event that follows a reasonable temporal sequence from administration of the study intervention follows a known or expected response pattern to the suspected intervention, but that could readily have been produced by a number of other factors.
- **Not Related:** The adverse event is clearly not related to the investigational agent/procedure - i.e., another cause of the event is most plausible; and/or a clinically plausible temporal sequence is inconsistent with the onset of the event and the study intervention and/or a causal relationship is

considered biologically implausible.

Note, given the nature of this pragmatic study, all deaths and hospitalizations will be considered expected and not related to the study.

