#### **Reporting schedule:**

- All **adverse events that are serious (SAE) and unexpected** (i.e., have not been previously reported for CST) will be reported to the IMPACT Collaboratory Regulatory and Data Team and NIA IMPACT Collaboratory PO for dissemination to the project's IMPACT Safety Officer within 48 hours of the study's knowledge of SAE.
  - o Only those adverse events that are serious (SAE), unexpected, **and related to the intervention** must also be reported to Advarra IRB. Unexpected and **unrelated** SAEs will be reported to Advarra IRB on a case-by-case basis if requested by the IMPACT Collaboratory Safety Officer or NIA IMPACT Collaboratory PO.
- All **unexpected** deaths will be reported to IMPACT Collaboratory Regulatory and Data Team and NIA IMPACT Collaboratory PO ([name]) for dissemination to the IMPACT Collaboratory Safety Officer within 24 hours of study's knowledge of death.
  - o Advarra IRB does not require the specific reporting of death outside of the SAE reporting requirement above, but they will be notified on a case-by-case basis if requested by the IMPACT Collaboratory Safety Officer or NIA IMPACT Collaboratory PO.
- All **unanticipated problems (UPs)** will be reported to the IMPACT Collaboratory Regulatory and Data Team and NIA IMPACT Collaboratory PO for dissemination to the project's IMPACT Collaboratory Safety Officer and IRB (if required) within 48 hours of the study's knowledge of the event.
- The summaries of all AEs, SAEs, deaths, and UPs will be reported to the IMPACT Collaboratory Regulatory and Data Team, NIA IMPACT Collaboratory PO, and the IMPACT Collaboratory Safety Officer 6 months after the start or enrollment and at the end of enrollment/data collection (whichever comes later), or at a frequency requested by the IMPACT Collaboratory Safety Officer or NIA IMPACT Collaboratory PO.

The timelines established above will allow for the study team to adhere to the reporting schedule required by the IMPACT Collaboratory. Additionally, all AEs, SAEs, and UP will be tracked in a log stored in the regulatory binder. All AEs, SAEs, and UP will be reviewed at the biweekly Quality Control Committee.

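### A blanket note classes every death and hospitalization as expected and unrelated, which removes case-level causality assessment and expedited notice for these events and contradicts the protocol's own definition of an unexpected SAE

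*Combined protocol and SAP*

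**What the plan says.** **The note.** The Relatedness part of section 7.3.1 ends by declaring that "all deaths and hospitalizations will be considered expected and not related to the study". It gives the pragmatic nature of the study as its reason and allows no exception.

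**The routes it touches.** The Reporting schedule in the same section sets these:
- Unexpected "deaths will be reported to IMPACT Collaboratory Regulatory and Data Team" and onward to the Safety Officer "within 24 hours of study's knowledge of death".
- SAEs that are also unexpected go to the same bodies "within 48 hours of the study's knowledge of SAE". Here unexpected is glossed as "i.e., have not been previously reported for CST".
- IRB reporting is mandatory only when an SAE is both unexpected and related. Other SAEs and deaths reach the IRB only if the Safety Officer or program officer asks.
- Unanticipated problems are due in 48 hours. Section 7.3 requires these to be unexpected and at least possibly related.

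**Case-level assessment.** Section 7.3.1 has the referring provider review the form and "complete the form with a determination on relatedness and severity". Under Relatedness, all adverse events "will have their relationship to V-CST assessed by a V-CST facilitator". Section 7.3.1 also says that facilitators and referring sites will assess hospitalizations and deaths.

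**Capture.** Section 7.3 covers both arms: "In the event of hospitalizations or death of any study participant (intervention or control group) identified by the referral site", the site reports it to the coordinating site.

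**The concern.** Sections 7.3 and 7.3.1 express a reasonable prior belief: deaths and hospitalizations occur in this population and are unlikely to be caused by the study. The note turns that belief into a fixed classification, made before any event is seen. A reporting rule that is triggered by unexpectedness or relatedness then cannot be triggered by these events.

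A linked event is conceivable on the protocol's own terms. Sections 5.1, 7 and 8 foresee distress during sessions. Section 5.2 describes physical movement at the start of sessions and says it is limited partly for safety. A hospitalization following such an event might meet the protocol's definition of possibly related, yet the note would require it to be recorded as unrelated, with no expedited notice. The waiver of informed consent in section 11.2 rests on minimal risk, so the safety record that supports this should come from assessment of the cases.

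**Working it through.** The point is one of logic, and the plan gives no figure to reproduce. The check applies the note to each route in turn, then repeats it with the Reporting schedule's gloss.

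| Route | Trigger | Death or hospitalization under the note | Under the gloss plus section 7.3 |
|---|---|---|---|
| 24-hour death report | death, unexpected | no death can qualify | the gloss is not attached to this rule |
| 48-hour SAE report | serious, unexpected | cannot qualify | every SAE qualifies |
| Mandatory IRB report | serious, unexpected, related | cannot qualify | still closed, because relatedness is fixed as absent |
| 48-hour unanticipated problem | unexpected, at least possibly related | cannot qualify | still closed, for the same reason |
| Log, biweekly review, periodic summaries | none | still applies | still applies |

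**Why the gloss reverses the second row.** The gloss makes an SAE unexpected if it has not been reported before for CST. Section 7.3 says no AE or SAE of CST has been reported in over 15 years of studies. Together these make every SAE unexpected, deaths and hospitalizations included. The note says the opposite, and staff cannot follow both.

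**A third standard.** The Expectedness part of section 7.3.1 calls an event expected if it is known to be associated with the intervention or the condition. That test is wider than the gloss, which looks at CST alone, and narrower than the note, which covers every cause.

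**A fourth inconsistency.** Section 7.3.1 requires immediate submission for events that are serious *and* unexpected. Section 10.3.2 says serious *or* unexpected. With *or*, a death qualifies even if it is classed as expected.

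**What remains.** Section 10.3.3 sums AE counts over V-CST participants and demographic sub-populations. No section states a comparison of deaths or hospitalizations between arms.

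**Could a comparison by arm replace case review?** The documents give no event rate, so the control rates below are assumptions. Arm sizes are 112 control and 56 intervention (section 9.2). Expected events at a common rate p are 168 × p. Power to detect a doubling, at two-sided 5%, is Φ[(|p₂ − p₁| − 1.96·SE₀)/SE₁], with SE₀ pooled and SE₁ unpooled.

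At p₁ = 0.05 and p₂ = 0.10:
- pooled rate = (112 × 0.05 + 56 × 0.10)/168 = 0.0667
- SE₀ = √[0.0667 × 0.9333 × (1/112 + 1/56)] = 0.0408
- SE₁ = √[0.05 × 0.95/112 + 0.10 × 0.90/56] = 0.0451
- power = Φ[(0.05 − 0.0800)/0.0451] = Φ(−0.67) = 25%

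| Assumed control rate | Expected events in 168 | Power for a doubling |
|---|---|---|
| 2% | 3.4 | 14% |
| 5% | 8.4 | 25% |
| 10% | 16.8 | 44% |
| 20% | 33.6 | 78% |

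Even at 2%, the chance of at least one event is 1 − 0.98¹⁶⁸ = 97%, so the note would very probably be used. Unless events are common, a comparison by arm is descriptive and cannot stand in for judgment of single cases.

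**The case against.** The strongest reply is that little is lost. The intervention is a referral to online group discussion, described throughout as minimal risk. Sites report deaths and hospitalizations in both arms. All AEs and SAEs are logged and reviewed every two weeks. Summaries go to the Safety Officer six months after enrollment starts and at the end, or as often as requested. Section 7.4 lets the PI, Safety Officer and IRB suspend or change the study. All of this stands, and it rules out three stronger readings that a reader might infer:

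- *That the note removes any check that could show harm.* It does not. Detection and aggregate review do not depend on expectedness or relatedness. What goes is the causality judgment on each case and the expedited notice.
- *That these events are never assessed.* Section 7.3.1 says they will be. The difficulty is that the note fixes the outcome of that assessment.
- *That the 48-hour SAE route is certainly empty for them.* The gloss supports the opposite result, so the finding there is a contradiction.

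Nor is every safety conclusion fixed in advance. Other SAE categories in section 7.3, such as disability or a life-threatening event, remain open to case-level grading unless they also involve death or hospitalization.

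On the assessing role, the two texts might describe a sequence in which the facilitator gives a first view and the provider completes the form. The protocol does not say so, and clarification is still needed. Whether the note would satisfy the NIA guidance cited under Expectedness cannot be judged from these documents.

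**Conclusion.** The plan is wrong as written on this point. Taken at its word, the note leaves the 24-hour unexpected-death rule with no possible case. It closes the unanticipated-problem and mandatory IRB routes to every death and hospitalization, whichever meaning of unexpected is used, because relatedness is ruled out. It overrides the case-level grading required elsewhere in section 7.3.1, and it conflicts with the gloss that governs the 48-hour SAE rule.

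The consequence is bounded: loss of case-level causality assessment and expedited notice for two event types. Aggregate review remains, without a stated comparison by arm. The conclusion follows from the text alone. Only the illustration of event counts and power rests on assumed rates. H1 to H5 are not affected.

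**What to change.** 1. Delete the blanket note. Classify each death and hospitalization case by case under the existing expectedness and relatedness definitions. Relatedness to V-CST applies to intervention-arm participants; it has little meaning for controls. The statements in sections 7.3 and 7.3.1 that such events are unlikely to be related can stay as expectations.
2. Reconcile section 7.3, section 7.3.1 (reporting process, Expectedness, Relatedness and Reporting schedule) and section 10.3.2 on three things: one meaning of unexpected, whether immediate reporting needs serious *and* unexpected or serious *or* unexpected, and which role makes the final relatedness determination.
3. In the summaries already planned, tabulate deaths and hospitalizations by randomized arm, with 56 and 112 as denominators if enrollment is as planned. State that facilitator contact may raise ascertainment in the intervention arm: facilitators pass such events to the referring physician, and controls have no such contact. Present the table as descriptive.

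The cost is wording changes, a short form entry per event and one table in reports that are already due. No new data source is needed.

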#### **Reporting schedule:**

- All **adverse events that are serious (SAE) and unexpected** (i.e., have not been previously reported for CST) will be reported to the IMPACT Collaboratory Regulatory and Data Team and NIA IMPACT Collaboratory PO for dissemination to the project's IMPACT Safety Officer within 48 hours of the study's knowledge of SAE.
  - o Only those adverse events that are serious (SAE), unexpected, **and related to the intervention** must also be reported to Advarra IRB. Unexpected and **unrelated** SAEs will be reported to Advarra IRB on a case-by-case basis if requested by the IMPACT Collaboratory Safety Officer or NIA IMPACT Collaboratory PO.
- All **unexpected** deaths will be reported to IMPACT Collaboratory Regulatory and Data Team and NIA IMPACT Collaboratory PO ([name]) for dissemination to the IMPACT Collaboratory Safety Officer within 24 hours of study's knowledge of death.
  - o Advarra IRB does not require the specific reporting of death outside of the SAE reporting requirement above, but they will be notified on a case-by-case basis if requested by the IMPACT Collaboratory Safety Officer or NIA IMPACT Collaboratory PO.
- All **unanticipated problems (UPs)** will be reported to the IMPACT Collaboratory Regulatory and Data Team and NIA IMPACT Collaboratory PO for dissemination to the project's IMPACT Collaboratory Safety Officer and IRB (if required) within 48 hours of the study's knowledge of the event.
- The summaries of all AEs, SAEs, deaths, and UPs will be reported to the IMPACT Collaboratory Regulatory and Data Team, NIA IMPACT Collaboratory PO, and the IMPACT Collaboratory Safety Officer 6 months after the start or enrollment and at the end of enrollment/data collection (whichever comes later), or at a frequency requested by the IMPACT Collaboratory Safety Officer or NIA IMPACT Collaboratory PO.

The timelines established above will allow for the study team to adhere to the reporting schedule required by the IMPACT Collaboratory. Additionally, all AEs, SAEs, and UP will be tracked in a log stored in the regulatory binder. All AEs, SAEs, and UP will be reviewed at the biweekly Quality Control Committee.

#### **7.3.2 Follow-up for Adverse Events**

Although the risks of participating in CST are minimal, it is possible that the group discussion that takes place during CST will increase participant stress. Increased stress is a possible mild AE of CST. AE reporting will follow the schedule and methods detailed in section 7.3.1. The referring physician will follow up with participants following an AE according to standard of care practice.

#### **7.4 Data and Safety Monitoring Plan**

This study will be monitored by an IMPACT/NIA appointed Safety Officer (SO). The PI will be responsible for monitoring and protecting the data under the laws of HIPAA. They will ensure that those involved in the study are adhering to the study protocol that is provided to the Institutional Review Board (IRB) and will conduct safety reviews according to the schedule above. During these review processes,

the PI will assess whether the study's protocol should continue unchanged, require amendments, or close to enrollment. Changes in protocol will only be made in the interest of protecting participants' safety. Before these changes are made, the PI will inform the IRB. The PI, Safety Officer, and the IRB will have the authority to stop or suspend the study or require modifications. All research methods will only be carried out by trained professionals who have completed the training module "Ethics on Human Research."

The outcome data will be collected in standard care and abstracted from the sites' clinical records for this study. The V-CST practitioners and Site Lead and Coordinators are appropriately trained medical professionals to deliver these interventions and address any complications should they arise. In terms of risks unrelated to health, there is low risk associated with collection and attainment of subjects' protected health information (PHI). These risks will be mitigated by the study team's adherence to the adequate plans that have been designed to prevent against the improper use and disclosure of identifying information.

To protect confidentiality, all PHI will be maintained in a HIPAA compliant Sharepoint file, all data will be deidentified at UMass before being transferred to Brown University for analysis, and all results will be published as group data to avoid using identifying information. UMass will be the primary location for all data management, maintenance, and distribution. Any identifying information will be destroyed at the earliest opportunity, unless such retention is required by law in the interests of patient safety. Lawful authorities will include members overseeing the research, such as the IRB and SO. In the event of illegal disclosure, the event will be documented in the "accounting for disclosures log" and participants will be subsequently made aware of the disclosure.

Raw data will be extracted from the research sites electronic medical record each participant's name, age, ICD-10 dementia diagnosis code(s), psychotropic medications and dosages, and cognitive test scores. These data will be stored in a HIPAA-compliant Sharepoint file. The referring sites will be granted access to upload their patient data, and access to patient data will be restricted to the PI and study coordinator. Sharepoint is an encrypted secure file transfer platform maintained by the UMass IT department, with access to Sharepoint granted and maintained by the UMass IT department. All data will then be transferred from Sharepoint into MS teams to be maintained and clean accessible to only the UMB team. Sharepoint will only be used to transfer data and will not be the primary storage platform. MS teams is a HIPAA compliant and password protected platform maintained and stored on a UMass IT server.

Data previous stored at UMB will be transferred via Sharepoint to UMass to be permanently stored/maintained by the UMass study team and PI. All UMB servers will be scrubbed of all data for this project and will not store any data.

